### Objectives and hypothesis

The primary objective of this prospective randomized double-blind trial is to evaluate the effect of LRR on AKP after TKA with patellar replacement when compared to the resurfaced patella without release.

The secondary objectives are to assess and compare the functional and radiological outcomes between the groups after 12 months.

The hypothesis is that LRR would decrease the incidence of AKP after TKA with patellar resurfacing, as well as it would improve functional outcomes.

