### **Data collection and outcome measures**

Preoperatively, demographic data regarding age, gender, body mass index and laterality will be recorded. At the preoperative visit and at the 1-year follow up, the following clinical and radiological data will be collected by an examiner blinded to the surgical technique performed:

[figure not shown]
- Patellar pain and function are evaluated with the patellofemoral score designed by Feller et al. The score is distributed with a maximum of 15 points for the intensity of anterior knee pain, 5 points for quadriceps strength, 5 points for the ability to rise from a chair and 5 points for stair-climbing ability.
- The Knee Society Score (KSS) for both the Knee and the Function scores, 0 being the worst and 100 the best possible result in each section.
- The pressure pain threshold (PPT) determined using pressure algometry (PA). The PPT is assessed 3 times in each knee, with a calibrated electronic algometer (Algometer, Somedic Sales, Hörby, Sweden) with a  $1\text{cm}^2$  probe placed perpendicular to the skin in the center of the anterior aspect of patella. The evaluator increases the pressure 20 kPa/s until the sensation become painful and the patient says “stop”. The final PPT value taken is the average of the 3 measurements.
- The Visual Analogue Scale (VAS) referred by the patients at rest, when walking and when going up and downstairs.

- Patellar height. Measured in the lateral view using the Caton-Deschamps index and its application in TKA.

**Figure 1.** Patellar height measurement defined as the ratio of the length of the patellar articular surface (B) and the distance between the lower pole of patellar articular surface and the anterior border of the tibial plateau (A) preoperatively or the tibial component surface postoperatively (A').

- Patellar tilt. Defined in the axial view, as the angle subtended by the anterior intercondylar line and the equatorial line of the patella preoperatively or a line drawn through the prosthesis-bone interface postoperatively.

**Figure 2.** Patellar tilt measurement.

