### Statistical analysis

The sample size calculation of 110 patients in each group was based on assuming a minimum difference of 1 point in the VAS value with a standard deviation of 2.5. A probability level of 0.05, a power of 80% and a drop-out rate of 10% were assumed.

Descriptive statistics were used for the demographic data. Continuous variables and measured scores were presented as mean and standard deviations and categorical variables as number and percentage. Between group comparisons were evaluated with the Mann-Whitney U test. These comparisons were performed with the preoperative and postoperative measurements. Differences between the groups in terms of changes or improvements (post vs. pre) were also assessed with the Mann-Whitney U test.

STATA version 15.1 (StataCorp, College Station, TX, USA) was used for the statistical analysis with p values of 0.05 being considered statistically significant.

For the calculation of intraclass correlation coefficients (ICC) two-way random-effects model approximation was performed, being in terms of *Shrout and Fleiss* notation ICC(2,1) for intrarater agreement and ICC(2,2) for interrater agreement.

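### Interrater agreement is planned as ICC(2,2), the reliability of a two-rater mean, although no two-rater mean is described; for single-reader values it overstates reliability

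*Combined protocol and SAP*

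**What the plan says.** Under Statistical analysis, the plan bases its reliability coefficients on a two-way random-effects model ("two-way random-effects model approximation was performed") and, citing Shrout and Fleiss notation, specifies "ICC(2,1) for intrarater agreement and ICC(2,2) for interrater agreement". It does not say which measurements these coefficients cover.

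Under Data collection and outcome measures, the introduction to the outcome list reads "the following clinical and radiological data will be collected by an examiner blinded to the surgical technique performed". The two radiographic entries define what is measured but not by how many readers:

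- Patellar height: "Measured in the lateral view using the Caton-Deschamps index and its application in TKA".
- Patellar tilt: "Defined in the axial view, as the angle subtended by the anterior intercondylar line and the equatorial line of the patella preoperatively", with a corresponding line for the postoperative film.

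The only averaging rule in the document concerns the pressure pain threshold: "The final PPT value taken is the average of the 3 measurements". That averages repeat readings, not raters.

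**The concern.** ICC(2,1) is the reliability of one measurement by one rater. ICC(2,2) is the reliability of the average of two raters, and it is always the higher of the two when agreement is positive but imperfect. The coefficient that describes a trial's data is the one whose form matches the value that enters the analysis.

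The plan describes a single examiner and no averaging over raters, yet chooses the averaged form for interrater agreement. An interrater ICC needs at least two raters, so the plan leaves open whose reading is analysed. If it is one reader's, two things follow:

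- The reported interrater figure exceeds the reliability of the values compared between groups.
- Interrater agreement can look as good as, or better than, intrarater agreement only because the two coefficients have different forms.

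If the second 2 was meant merely as a label for two raters, the notation is wrong and needs correcting.

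The objectives include "The secondary objectives are to assess and compare the functional and radiological outcomes between the groups after 12 months". If the ICCs cover the radiographic measurements, readers will use them to judge how far those secondary results can be trusted.

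**Working it through.** **Inputs.** From Statistical analysis: the two-way random-effects model, the single-measurement form for intrarater agreement, and the two-rater-mean form (k = 2) for interrater agreement. The document gives no ICC value, number of readers or size of reliability sample, so there is no stated ICC to reproduce. All values of r below are assumptions.

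**Relation between the two forms.** Let BMS, JMS and EMS be the mean squares for subjects, raters and error, with n subjects and k = 2 raters. Then

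- ICC(2,1) = (BMS − EMS) / [BMS + EMS + 2(JMS − EMS)/n]
- ICC(2,2) = (BMS − EMS) / [BMS + (JMS − EMS)/n]

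Write A = BMS − EMS and D = BMS + (JMS − EMS)/n. The denominator of ICC(2,1) equals 2D − A, so with r = ICC(2,1) and R = ICC(2,2):

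- R = A/D and r = A/(2D − A)
- hence R = 2r/(1 + r) and r = R/(2 − R)

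This is an exact identity between the two estimates. A simulation of 220 subjects and two raters (2,000 runs, with a rater effect) agreed with it to machine precision; the mean coefficients were 0.601 and 0.749.

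**Forward: what the plan would report for a given single-rater value.**

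| Assumed ICC(2,1) | ICC(2,2) = 2r/(1 + r) | Excess |
|---|---|---|
| 0.50 | 1.00/1.50 = 0.667 | 0.167 |
| 0.60 | 1.20/1.60 = 0.750 | 0.150 |
| 0.70 | 1.40/1.70 = 0.824 | 0.124 |
| 0.80 | 1.60/1.80 = 0.889 | 0.089 |
| 0.90 | 1.80/1.90 = 0.947 | 0.047 |

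**Upper bound.** The excess is r(1 − r)/(1 + r). Setting its derivative to zero gives 1 − 2r − r² = 0, so r = √2 − 1 = 0.414, where the excess is 3 − 2√2 = 0.172. The overstatement therefore cannot exceed 0.172 for any positive r, and above r = 0.414 it shrinks as agreement improves.

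**Reverse: what a reported figure means for one reader.**

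| Reported ICC(2,2) | ICC(2,1) = R/(2 − R) |
|---|---|
| 0.75 | 0.75/1.25 = 0.600 |
| 0.80 | 0.80/1.20 = 0.667 |
| 0.90 | 0.90/1.10 = 0.818 |
| 0.95 | 0.95/1.05 = 0.905 |

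**Effect on the comparison of intrarater with interrater agreement.** Reported values of 0.90 for both would look equal, but on the single-measurement scale they are 0.90 and 0.818. The order can even reverse: an intrarater value of 0.75 and a single-rater interrater value of 0.70 would be shown as 0.75 and 0.82.

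**What is not affected.** The sample size of 110 per group follows from a difference of 1, an SD of 2.5, two-sided 0.05 and 80% power: 2 × (1.96 + 0.8416)² × 2.5² / 1² = 98.1, rounded up to 99, and 99/0.9 = 110. No ICC enters this calculation or the Mann-Whitney comparisons.

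**The case against.** The strongest reply is that the document shows an omission, not an error. The authors name the notation and deliberately give the two coefficients different second indices, which fits a plan to average two readers as well as it fits a slip. The reference to one examiner is there to establish blinding and covers all clinical and radiological data at once. Since an interrater ICC already implies a second rater for something, the singular cannot be taken literally for every measurement. Moreover, the coefficients are labelled, so an informed reader can convert one form to the other. The size of the problem is assumed throughout, and the largest gaps arise at levels of agreement that nothing in the document supports.

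Much of this is fair and limits the point. It is not established that single-reader values will be analysed, and if two readers are averaged there is no overstatement. In that case the two coefficients would simply describe different quantities, each correctly labelled. It is also true that no decision in the plan depends on a reliability threshold.

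The reply does not supply the missing link. Nothing in the document defines an analysed value as a two-rater mean, although the authors do state an averaging rule for the pressure pain threshold. The missing figures are no reason to assume such a rule; the surviving captions concern how height and tilt are measured. The data as described are single-examiner values, and the coefficient chosen does not describe those. Labels help only readers who know the notation and do the conversion.

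**Conclusion.** The point holds as a conditional one, and it is minor. That ICC(2,2) is the reliability of a two-rater mean, and that the plan states no such mean, are both certain. Whether reliability will actually be overstated depends on whose value is analysed, which the plan does not settle.

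If a single reader's value is analysed, the excess is about 0.05 at an assumed single-rater ICC of 0.90, 0.12 at 0.70 and 0.17 at 0.50. If a two-reader mean is analysed, it is zero. In both cases the interrater and intrarater figures cannot be compared at face value. The consequence is confined to how measurement reliability is reported and read.

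**What to change.** In Statistical analysis, report interrater ICC(2,1) with its 95% confidence interval beside the intrarater ICC(2,1), so that both describe a single measurement. Retain ICC(2,2) as the main interrater figure only if the analysed value is the mean of two readers and Data collection and outcome measures says so.

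To make the choice checkable, add to that section the number of readers and whose value is analysed, and state in Statistical analysis which measurements the ICCs cover.

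This takes one or two sentences and uses the same data. The only cost is that the reported interrater figure will be less favourable.
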